1.2 Decitabine and Hypomethylating agents in AML/MDS

[REDACTED]

[REDACTED]

[REDACTED]

[REDACTED]

[REDACTED]

[REDACTED]

[REDACTED]

[Redacted]

[Redacted]	[Redacted]	[Redacted]
[Redacted]	[Redacted]	[Redacted]
[Redacted]	[Redacted]	[Redacted]
[Redacted]	[Redacted]	[Redacted]
[Redacted]	[Redacted]	[Redacted]
[Redacted]	[Redacted]	[Redacted]
[Redacted]	[Redacted]	[Redacted]
[Redacted]	[Redacted]	[Redacted]
[Redacted]	[Redacted]	[Redacted]
[Redacted]	[Redacted]	[Redacted]

[Redacted]

[Redacted]

1.2.2 Experience with extended dosing schedules

[Redacted]

1.3 Correlative Studies

All correlative studies will be collected under HRPO# 201011766 (“Tissue Acquisition for Analysis of Genetic Progression Factors in Hematologic Diseases”) that all patients will be concurrently enrolled in. The goals of the correlative studies include:

1. To correlate patient-specific mutations with response to decitabine.
We will perform exome sequencing of each patient’s pre-study bone marrow sample and skin sample. We will determine AML/MDS-associated variants found in the bone marrow, but not skin sample. We will correlate the presence of mutations with response (especially mutations in *DNMT3A*, *IDH1*, *IDH2*, and *TET2*). This study is powered to identify mutations with >80% sensitivity to predict decitabine response if used as a clinical assay.
2. To correlate the velocity and depth of response with response to decitabine.
We will assess tumor burden by allele frequency of patient-specific mutations in bone marrow samples collected pre study, Cycle 1 Day 10±1, Cycle 1 Day 28±4, and Cycle 2 Day 28±4. We will assess mutations in at least 24 recurrently mutated genes (including, but not limited to: *FLT3*, *DNMT3A*, *NPM1*, *TET2*, *WT1*, *IDH1*, *IDH2*, *RUNX1*, *NRAS*, *TP53*, *U2AF1*, *KRAS*, *PHF6*, *MSTP9*, *PTPN11*, *KIT*, *SMC3*, *PRUNE2*, *ETV6*, *CEBPA*, *SMC1A*, *ASXL1*, *STAG2*, *RAD21*) as well as all patient-specific mutations discovered during exome sequencing. The leukemic allele frequency will be measured using the Illumina MySeq or HiSeq platform using DNA capture by gene specific biotinylated-oligonucleotides. Patient bone marrow samples will be assessed pre-study, Cycle 1 Day 10 ± 1, Cycle 1 Day 28 ± 4, and Cycle 2 Day 28 ± 4 and compared with patient specific skin samples (normal control). The velocity of response will be calculated as the natural log rate of patient-specific mutation allele frequency clearance. Depth of response will be defined as the lowest patient-specific mutation

allele frequency in a bone marrow sample. The velocity and depth of tumor response will be correlated to:

- Achievement of clinical CR,
- Time to best response,
- Mutational status,
- Time to disease progression.

Because all patient-specific exome-discovered mutations will be assessed a second time in the primary bone marrow sample as well as the Cycle 1 Day 10 \pm 1, Cycle 1 Day 28 \pm 4, and Cycle 2 Day 28 \pm 4 bone marrow samples, this study will also serve to validate all exome-discovered mutations. This is important, because exome sequencing is associated with a 20-50% false-discovery rate depending on type I error tolerated (mutation-calling algorithms are typically set for greater sensitivity than specificity). Thus, many mutations discovered during exome sequencing are incorrect. This second analysis of these mutations will serve to exclude these false positive calls.

3. To correlate the bone marrow expression profile from pre-study and Cycle 1 Day 10 \pm 1 with response to decitabine.

We will correlate expression signatures, and changes in expression signatures, with:

- Achievement of clinical CR,
- Mutation status.

4. To correlate the extent of bone marrow DNA hypomethylation on Cycle 1 Day 10 \pm 1 with response to decitabine.

We will assess the percent reduction in bone marrow methylcytosine content using LC-MS. Patients will be evaluated pre-study and Cycle 1 Day 10 \pm 1. The change in DNA methylcytosine content will be correlated to:

- Achievement of clinical CR,
- Change in expression signature.

This will determine whether inadequate blast exposure to decitabine correlates with drug resistance.

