6.1 Delay for Cytopenia or Infection

As cytopenias are a defining feature of AML and MDS, their presence alone does not generally warrant dose modifications or delays. Patients will receive four cycles of therapy without adjustment for any cytopenia. Following Cycle 4, dose modifications or delays for cytopenias will be made at the discretion of the investigator.

Patients with febrile neutropenia (temperature $\geq 38.5^\circ$ with ANC $< 1,000/\mu\text{l}$) or systemic infections should have treatment held until clinical resolution of the infection.

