6.2 Delay for Organ Dysfunction

If renal dysfunction (creatinine $\geq 3 \times$ institutional upper limit of normal) or hepatic dysfunction (bilirubin $\geq 2.5 \text{ mg/dl}$ or ALT/AST $\geq 3 \times$ institutional upper limit of normal) occurs, therapy may not resume until the abnormalities have resolved to below the limits stated above. If renal or hepatic dysfunction occurs during a treatment course, the next dose of decitabine should be held, and serum chemistries should be checked twice per week. Decitabine can be resumed at full dose when creatinine, bilirubin, ALT and AST are below the limits listed above.

For grade 3-4 non-hematologic toxicities related to decitabine, decitabine treatment should be delayed until recovery to baseline or to grade ≤ 1 . Decitabine may be reintroduced with a 50% dose reduction, or at full dose at the discretion of the investigator.

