14.2.3 Secondary Endpoint Analyses

The overall response rate (CR/CRi/PR) and complete response rate (CR/CRi) will be compared with historical controls[2], and the 95% confidence intervals will be provided.

The rate of patient specific mutation clearance after 10, 28, and 56 days of therapy will be determined using an Illumina based platform. We will compare the rate of mutation clearance between the patients who achieve a CR/CRi after 4 cycles and those who do not. We anticipate that we will identify between 6 and 25 exonic SNVs per case (the range obtained with >200 AML samples sequenced to date with whole genome or exome sequencing), and that the expected 95% confidence interval of the mean variant allele frequency will be $\pm 2.56\%$ and $\pm 1.25\%$,

respectively, if we assume an anticipated standard deviation of 3.2% within the same clone. The change of tumor burden over time and its association with clinical response will be assessed using 2-way ANOVA for repeated measurement data, followed by the ad-hoc multiple comparisons for between-group differences (e.g., responders vs. non-responders) at given time points as well as the between-time differences within each group. The resultant critical P values will also be corrected using permutation analysis for multiple testing.

The percent decrease in bone marrow methylcytosine will be calculated on day 10 ± 1 . We will compare this reduction with previously published data and between the patients who achieve CR/CRi and those who do not. The correlation of peak plasma levels of decitabine with response will be assessed using 2-sample t-test or Mann-Whitney non-parametric rank-sum test as appropriate. The change of total bone marrow DNA methylcytosine from baseline and its association with both steady-state plasma drug levels and response will be assessed using 2-way ANOVA for repeated measurement data, followed by the ad-hoc multiple comparisons for between-group differences (e.g., responders vs. non-responders) and between-time differences. Similar analyses will be performed for the correlation of expression profiles and SNP analysis with pharmacokinetic data.

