5.0 INVESTIGATIONAL PLAN

5.1 Summary of Study Design

This is an open-label, single-arm, Phase II, biomarker study of patients with AML or MDS who are treated with 10 consecutive days of decitabine. FAB-M3 AML is excluded from this trial, because other well-tolerated options exist for the treatment of FAB-M3 acute promyelocytic leukemia. AML patients who are < 60 years old and have not received cytotoxic induction chemotherapy are also excluded, because cytotoxic therapy offers a curative possibility for these patients. MDS patients without cytopenias are also excluded because these patients can be followed with watchful-waiting.

All patients will undergo bone marrow biopsies pre-study, on Cycle 1 Day 10 \pm 1, and on Day 28 \pm 4 of Cycles 1, 2, 4, and 6. Following Cycle 6, bone marrow biopsies should be performed at the discretion of the treating physician to assess for relapse or progression. Patients will provide a skin biopsy sample pre-study. See Section 8.0 for details on correlative studies.

Patients will receive decitabine 20 mg/m²/day as a 1-hour infusion on consecutive Days 1-10 in 28-day cycles. The dose will be calculated based on actual patient weight at the beginning of each cycle.

Once AML patients achieve morphologic complete remission with incomplete blood count recovery (CRi) or MDS patients achieve a marrow complete response (Marrow CR) as defined in Section 9.0, decitabine administration may be decreased to 20 mg/m²/day for ten consecutive days every 6 weeks, to limit myelosuppressive toxicity and improve count recovery. After 2 cycles at 6 week intervals, the dose may be reduce to 20 mg/m²/day for five consecutive days in 6 week cycles, at the discretion of the treating physician. After two cycles of five consecutive days of treatment, if the patient meets the definition of CR with complete cytogenetic response as defined in Section 9.0, administration may further be decreased to three consecutive days per cycle at the discretion of the treating physician.

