6.2 Delay for Organ Dysfunction

If renal dysfunction (creatinine $\geq 3 \times$ institutional upper limit of normal) or hepatic dysfunction (bilirubin ≥ 2.5 mg/dl or ALT/AST $\geq 3 \times$ institutional upper limit of normal) occurs, therapy may not resume until the abnormalities have resolved to below the limits stated above. If renal or hepatic dysfunction occurs during a treatment course, the next dose of decitabine should be held, and serum chemistries should be checked twice per week. Decitabine can be resumed at full dose when creatinine, bilirubin, ALT and AST are below the limits listed above.

For grade 3-4 non-hematologic toxicities related to decitabine, decitabine treatment should be delayed until recovery to baseline or to grade ≤ 1 . Decitabine may be reintroduced with a 50% dose reduction, or at full dose at the discretion of the investigator.

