14.2.3 Secondary Endpoint Analyses

The overall response rate (CR/CRi/PR) and complete response rate (CR/CRi) will be compared with historical controls[2], and the 95% confidence intervals will be provided.

The rate of patient specific mutation clearance after 10, 28, and 56 days of therapy will be determined using an Illumina based platform. We will compare the rate of mutation clearance between the patients who achieve a CR/CRi after 4 cycles and those who do not. We anticipate that we will identify between 6 and 25 exonic SNVs per case (the range obtained with >200 AML samples sequenced to date with whole genome or exome sequencing), and that the expected 95% confidence interval of the mean variant allele frequency will be $\pm 2.56\%$ and $\pm 1.25\%$,

respectively, if we assume an anticipated standard deviation of 3.2% within the same clone. The change of tumor burden over time and its association with clinical response will be assessed using 2-way ANOVA for repeated measurement data, followed by the ad-hoc multiple comparisons for between-group differences (e.g., responders vs. non-responders) at given time points as well as the between-time differences within each group. The resultant critical P values will also be corrected using permutation analysis for multiple testing.

The percent decrease in bone marrow methylcytosine will be calculated on day 10 ± 1 . We will compare this reduction with previously published data and between the patients who achieve CR/CRi and those who do not. The correlation of peak plasma levels of decitabine with response will be assessed using 2-sample t-test or Mann-Whitney non-parametric rank-sum test as appropriate. The change of total bone marrow DNA methylcytosine from baseline and its association with both steady-state plasma drug levels and response will be assessed using 2-way ANOVA for repeated measurement data, followed by the ad-hoc multiple comparisons for between-group differences (e.g., responders vs. non-responders) and between-time differences. Similar analyses will be performed for the correlation of expression profiles and SNP analysis with pharmacokinetic data.

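### The Day 10 methylcytosine comparison ignores how many infusions were given, so held doses in sick patients could mimic a link between low hypomethylation and resistance

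*Combined protocol and SAP*

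**What the plan says.** The relevant text is the same in every protocol version in the file.

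- **Timing of the measurement.** Section 1.3: "Patients will be evaluated pre-study and Cycle 1 Day 10" ± 1. Section 14.2.3: "The percent decrease in bone marrow methylcytosine will be calculated on day 10" ± 1. Neither asks for a minimum number of doses before the marrow.
- **Planned dosing.** Section 5.1 gives decitabine "as a 1-hour infusion on consecutive Days 1-10 in 28-day cycles".
- **Holds.** Section 6.2: "If renal or hepatic dysfunction occurs during a treatment course, the next dose of decitabine should be held". For grade 3-4 non-hematologic toxicity related to the drug, the same section says "decitabine treatment should be delayed until recovery to baseline or to grade" 1 or lower. Section 6.1 says that patients with febrile neutropenia or "systemic infections should have treatment held until clinical resolution of the infection".
- **Comparison.** Section 14.2.3: "We will compare this reduction with previously published data and between the patients who achieve CR/CRi and those who do not". The change from baseline is also to be analysed by two-way repeated-measures ANOVA. No covariate, stratum or exclusion for doses received is named.
- **Inference.** Section 1.3: "This will determine whether inadequate blast exposure to decitabine correlates with drug resistance".
- **Dose data.** Exposure is summarised only in the safety analysis (14.2.4). The Treatment Record Form (section 15.0) is kept throughout treatment.

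**The concern.** The comparison treats the Day 10 fall as a measure of what decitabine did to the marrow. It is also a measure of how much decitabine was given. A patient whose doses were held in the first week reaches Day 10 with less drug on board and, other things equal, a smaller fall. The same illness can make CR/CRi less likely for reasons unrelated to drug sensitivity. The two groups would then differ in methylcytosine reduction even if, at equal dosing, the reduction had no bearing on response.

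Nothing else in the plan separates drug not given from drug given without effect. The efficacy-evaluable set (14.1) requires one cycle of treatment, but this is not defined in doses and the set is not assigned to this analysis. The logistic adjustment in 14.2.2 belongs to the primary analysis and does not name dose. A Day 4 plasma sample is described in only one of the versions. The others still mention plasma levels in 14.2.3 but describe no sample, and one Day 4 concentration would not count doses in any case.

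At stake is the reading of a named secondary objective (2.2): whether a small fall means resistance or missed infusions.

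**Working it through.** **The plan's own figure.** Section 14.2.3 gives 99% power for a 20-point difference, with SD 15, 45 responders, 55 non-responders and alpha 0.05 (taken as two-sided), based on a two-sample t-test.

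- SE = 15 × √(1/45 + 1/55) = 3.02 points.
- 20 / 3.02 = 6.6 standard errors, so power exceeds 99.9%. The stated 99% is reproduced and is conservative.
- An observed difference of about 1.98 × 3.02 = 6.0 points is already significant.

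**Assumptions, none of them in the documents.** Proportion held before the Day 10 marrow, h: 10-30%. Response among held patients, r: 20-30%, with 45% overall as in the plan. Reduction lost through missed doses, d: 10-20 points. Among patients with equal dosing, no association between reduction and response.

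**Induced difference** = d × [P(held | non-responder) − P(held | responder)] = d × [h(1 − r)/0.55 − h·r/0.45].

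- Low (10%, 30%, 10): 10 × (0.127 − 0.067) = 0.6 points.
- Middle (20%, 20%, 15): 15 × (0.291 − 0.089) = 3.0 points.
- High (30%, 20%, 20): 20 × (0.436 − 0.133) = 6.1 points.

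**False-positive rate at nominal 5%.** If SD 15 is the total SD, the noncentral t applies directly. If SD 15 is the residual SD, holds add d²·p(1 − p) to the variance within each group, where p is that group's held proportion.

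- Middle: the added variance is 18.2 in responders and 46.4 in non-responders. SE = √(243.2/45 + 271.4/55) = 3.22, ratio 3.03/3.22 = 0.94, rate about 15%.
- High: the added variance is 46.2 and 98.4. SE = √(271.2/45 + 323.4/55) = 3.45, ratio 6.06/3.45 = 1.76, rate about 41%. Simulation with group sizes left to vary gives about 39%.

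| Held | Response if held | Points lost | Difference | Rate, SD 15 total | Rate, SD 15 residual |
|---|---|---|---|---|---|
| 10% | 30% | 10 | 0.6 | 5.5% | about 5-6% |
| 10% | 20% | 20 | 2.0 | 10% | 9-10% |
| 20% | 20% | 15 | 3.0 | 17% | 15% |
| 30% | 20% | 20 | 6.1 | 51% | about 41% |

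**Effect of the remedy.** In simulation under the same model, repeating the test without held patients brought the rate back to about 5% in every scenario, as did a covariate for being held. In the high case, 45 − 6 = 39 responders and 55 − 24 = 31 non-responders remain, and power for 20 points is still above 99.9%.

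**The case against.** **The question is about exposure.** A patient given fewer doses really has had inadequate exposure, and section 1.3 claims only a correlation. Replacing the planned analysis with a dose-adjusted one would remove part of what is being studied. This stands. The unadjusted comparison should stay, and the dose-restricted one should sit beside it.

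**Early holds may be rare.** Active infection is an exclusion, bilirubin, AST/ALT and creatinine are capped at entry, and cytopenia alone triggers no adjustment for four cycles. This stands too. At 10% held, the assumed range gives false-positive rates of only about 5-10%.

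**Mid-course holding.** A reader might infer that both sections plainly stop dosing within a course. Only the renal and hepatic rule says so. The infection rule says that treatment is held, under a heading about delay.

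**Size.** A reader might infer that held doses could manufacture the effect the study is powered for. The figures do not support that. Even with 10% response among held patients and 30 points lost, at 30% held, the difference is 30 × (0.491 − 0.067) = 12.7 points, short of 20. It could reach significance, because about 6 points is enough.

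**Scope.** It is tempting to extend the point to all Day 10 biomarkers and to the ±1-day window. The documents attach no exposure-resistance claim to expression change or variant allele frequency, and allele frequency is also assessed at Days 28 and 56. The window adds noise but has no stated link to response.

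**Test.** Section 14.2.3 assigns methylcytosine change to repeated-measures ANOVA; the t-test appears for it only in the power text. The ANOVA as described takes no account of doses either, so the gap is the same.

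**Conclusion.** The gap is real but modest. The reduction is timed by calendar day, the protocol provides for doses to be held, and the comparison by CR/CRi takes no account of infusions received. An association could therefore arise from illness alone. Under the stated assumptions it would be 0.6 to 6.1 points, with a false-positive rate of about 5-41% (SD 15 residual) or 5.5-51% (SD 15 total). Every input on hold frequency, response in held patients and points lost is assumed, so these figures show what could happen, not what is likely.

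The documents do not support saying that the planned comparison is invalid or that its result would be an artefact. What they leave open is whether a positive result may be read as resistance at a given dose. The primary objective, mutation status against response, is unaffected. This is a cheap improvement to one secondary analysis.

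**What to change.** In section 14.2.3:

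1. Derive, from the Treatment Record Form, the number of infusions given before the Day 10 marrow.
2. Keep the planned unadjusted comparison of methylcytosine reduction by CR/CRi.
3. Prespecify a repeat in patients who had received all infusions scheduled up to their sample. An analysis with number of infusions as a covariate may be added.
4. Report both results, with the number of patients in each.

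In section 1.3, attribute low hypomethylation to resistance at a given dose only if the association persists in the fully dosed set. Otherwise describe it as possibly due to doses not given.

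The cost is one derived variable from data already collected, a few lines of analysis-plan text, and slightly fewer patients in the repeat. Extending the repeat to expression change is optional, and allele frequency need not be included. No dose, hold rule or visit changes.

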2.0 OBJECTIVES

2.1 Primary Objective

To determine whether patient-specific mutations correlate with clinical overall response to decitabine in patients with AML or MDS.

2.2 Secondary Objectives

- To determine whether 10 consecutive days per cycle of decitabine improves outcomes compared with historical controls treated with 5 consecutive days per cycle of decitabine.
- To determine whether other biomarkers correlate with clinical overall response to decitabine in patients with AML or MDS. These will include:
 1. The velocity and depth of patient-specific mutation clearance;
 2. The bone marrow expression profile and change in expression profile during decitabine treatment;
 3. The decrease in bone marrow methylcytosine content in response to decitabine.

3.0 PATIENT SELECTION

3.1 Inclusion Criteria

All of the following:

- Patient must have non-M3 AML or MDS
- An adverse risk karyotype defined by:
 - Complex karyotype by cytogenetics, or
 - Deletion of all or part of chromosome 5, 7, 12, or 17 defined by FISH or cytogenetics, or
 - Somatic TP53 mutation

All of the following:

1. Patient must have an ECOG performance status ≤ 2 .
2. Patient must have $>10\%$ disease burden measured by cytomorphology, flow cytometry, or cytogenetics.
3. Patient must have peripheral white blood cell count $\leq 50,000/\text{mcl}$.
4. Patient must have adequate organ function, defined as:
 - a. Total bilirubin $\leq 1.5 \times \text{ULN}$
 - b. AST/ALT $\leq 2.5 \times \text{ULN}$
 - c. Serum creatinine $\leq 2.0 \times \text{ULN}$
5. Patient must have undergone ≤ 2 cycles of prior hypomethylating agent (decitabine or azacitidine).
6. Patient must be enrolled in HRPO# 201011766 (“Tissue Acquisition for Analysis of Genetic Progression Factors in Hematologic Diseases”).
7. Patient must be ≥ 18 years of age.
8. Patient must be able to understand and willing to sign an IRB-approved written informed consent document.

3.2 Exclusion Criteria

1. Patient must not be pregnant or nursing.
2. The patient must not have acute promyelocytic leukemia or t(15;17) observed by FISH.
3. Patient must not have known CNS leukemia.
4. Patient must not have a history of positive HIV serology.
5. Patient must not have a history of positive Hepatitis C serology.
6. Patient must not have undergone a prior allogeneic stem cell transplant.
7. Patient must not have any uncontrolled intercurrent illness including, but not limited to, ongoing or active infection, ongoing or active GVHD, congestive heart failure of NYHA class 3 or 4, unstable angina pectoris, cardiac arrhythmia, or psychiatric illness/social situation that would limit compliance with study requirements.
8. Patient must not have had radiation therapy within 14 days of enrollment.
9. Patient must not have received any chemotherapy within 21 days of enrollment, and any acute treatment-related toxicities must have returned to baseline. Patients

may be receiving hydroxyurea at time of enrollment.

